6.2.2 Adjustment for Covariates

All models will be adjusted for the following potential confounders: age, sex, travel time to facility, illness duration, clinical presentations, previous care and previous treatment. Further sensitivity analysis may be performed adjusting for additional baseline variables.

6.2.3 Test of Assumptions, Actions to be taken

Continuous variables will be inspected using histograms: 1) to assess for outliers which may be queried for accuracy, and 2) to assess whether appropriate transformations are required for analyses.

As a multilevel logistic regression model is estimated using quadrature (rather likelihood methods), a quadrature check to test for adequate model fit will be performed. In case of unreliable model fit, generalized estimating equations will be used to fit the model which will provide population-averaged odds ratios and 95% confidence intervals.

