3.4 Sample Size

The sample size for the quasi-experimental pre-post study is calculated separately for each country, based on comparison between pre- and post-intervention periods. The following assumptions are used:

- ξ power 80%
- ξ alpha level of 0.05
- ξ pre-intervention referral to a higher level of care 3%, with a minimum detectable difference of 50%
- ξ pre-intervention antibiotic prescription of 60%
- ξ intra-cluster correlation coefficient (ICC) of 0.005 for referral and 0.05 for antimicrobial prescription
- ξ Kenya – estimated average cluster size of 230 children / month (assuming a cluster ratio of health centres : dispensaries 1:2, with 100 / month in dispensaries and 500 / month in health centres)
- ξ Senegal – estimated cluster size of 170 children per month

For the referral primary outcome, we therefore initially estimated requiring the following sample size:

- ξ Kenya – 17 facilities, recruiting an average of 690 children per quarter per facility, equating to 11,730 children per quarter
- ξ Senegal – 18 facilities, recruiting an average of 510 children per quarter per facility, equating to 9,180 children per quarter

For the antibiotic prescription primary outcome, this would enable a minimum detectable reduction of 18% in Kenya and Senegal.

Following lower than anticipated recruitment in the pre-intervention period, sample size calculation was revised. As a result, two additional facilities were added per country and the pre-intervention period was extended from an initially anticipated 3 months to a 6 – 8 month period. A decision was also taken to target a post-intervention sample size of at least the same as the pre-intervention sample size, as well as a minimum duration of 9 months post-intervention to allow for stabilisation over time and some seasonal overlap of pre- and post-intervention periods.

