4 STATISTICAL PRINCIPLES

4.1 Confidence Intervals and p-Values

Results estimates of primary and secondary outcomes will be presented along with the associated two-sided 95% confidence intervals.

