6.2 Analysis Methods

6.2.1 Analytical Methods

For the primary analysis, pre-intervention and post-intervention periods will be defined as follow:

Pre-intervention period: from the date of data collection start to the date healthcare providers left the facilities for training on the intervention

Post-intervention period: from the date healthcare providers returned to the facilities after training and the devices was delivered to the facilities to the end of data collection

As training was staggered for the facilities, the definitions above will be applied at the facility level.

Outcomes will be described for each time period using summary statistics. In particular, counts and percentages will be used for binary variables and reported with one decimal place; mean and standard deviation (SD) or median (IQR) for continuous variables depending on their

distribution. Mean and median will be displayed with one decimal place and SD and IQR will be presented with two decimal places.

The two primary outcomes will be assessed using a random effects logistic regression model with the cluster included as a random effect. If convergence issues arise due to sparse data, clusters may be dropped or combined to higher grouping level (e.g. district).

Results will be reported with odds ratios, risk differences and their associated 95% confidence intervals (CI).

Secondary outcomes and other binary outcomes of interest will be evaluated in the same way.

Other continuous outcomes of interest will be assessed using random effects linear regression model with the cluster included as a random effect. Results will be reported in terms of adjusted mean differences with associated 95% CIs.

Modelling of secondary outcomes will be performed if numbers allow.

Further exploratory analysis, including interrupted time series analysis to assess change over time and data linked between the quasi-experimental pre-post study and the SPA and time-flow studies. These fall outside the scope of this SAP and will be detailed in a separate document.

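### The GEE fallback in SAP 6.2.3 names no variance estimator, small-sample correction or reference distribution, although each country analysis rests on only 19 or 20 facilities

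*SAP*

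**What the plan says.** SAP 6.2.1 sets the main analysis: "The two primary outcomes will be assessed using a random effects logistic regression model with the cluster included as a random effect". Secondary and other binary outcomes are handled in the same way, with secondary outcomes modelled if numbers allow. Results are odds ratios and risk differences, with "associated two-sided 95% confidence intervals" under SAP 4.1.

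SAP 6.2.3 describes the model as "estimated using quadrature (rather likelihood methods") and then says "a quadrature check to test for adequate model fit will be performed". The consequence of a failed check is one sentence: "In case of unreliable model fit, generalized estimating equations will be used to fit the model which will provide population-averaged odds ratios", with 95% confidence intervals. Neither the SAP nor the protocol gives a working correlation, a variance estimator, a small-sample correction or a reference distribution for that GEE.

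On the number and size of clusters, SAP 3.4 starts from 17 facilities in Kenya and 18 in Senegal and adds that "two additional facilities were added per country". For Kenya it assumes one health centre to two dispensaries, "with 100 / month in dispensaries and 500 / month in health centres". SAP 3.7 and protocol 7.3 call for an analysis of each country as well as a pooled one.

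**The concern.** The robust (sandwich) standard error that usually accompanies GEE is justified when there are many clusters. With few, each facility pulls the fitted proportion towards its own data, so its residual is too small and the standard error is biased downwards. The bias grows when a few large facilities carry most of the children. Normal quantiles add to it, because they ignore the uncertainty in a variance estimated from about 19 units.

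So an analyst who follows 6.2.3 with the common default would report intervals that are too narrow, possibly for a primary outcome. Because the SAP is silent, the choice of standard error could also be made after the results are seen.

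**Working it through.** **1. The plan's own sample size.** Inputs from SAP 3.4 and protocol 6.6.1: referral 3% v 4.5%, "alpha level of 0.05" (taken as two-sided), power 80%, ICC 0.005, and 690 (Kenya) or 510 (Senegal) children per facility per period.

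- n per period without clustering = [1.960·√(2·0.0375·0.9625) + 0.842·√(0.03·0.97 + 0.045·0.955)]² / 0.015² = 2,518 after rounding up.
- Kenya: design effect 1 + 689 × 0.005 = 4.445. Then 2,518 × 4.445 / 690 = 16.2, so 17 facilities and 17 × 690 = 11,730 children.
- Senegal: design effect 1 + 509 × 0.005 = 3.545. Then 2,518 × 3.545 / 510 = 17.5, so 18 facilities and 18 × 510 = 9,180 children.

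Both match the plan. Power for the 18% antibiotic reduction comes out at 79.8% (Kenya) and 81.7% (Senegal), which also agrees. The later additions give 19, 20 and, pooled, 39 facilities.

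**2. How unequal the Kenya facilities are.** Over the initial three months, 500 and 100 per month become 1,500 and 300. With 6 large and 13 small facilities the total is 6 × 1,500 + 13 × 300 = 12,900. The effective number of equal-sized facilities is 12,900² / (6 × 1,500² + 13 × 300²) = 11.3. For a period-only model with independence working correlation, the leverage of a facility is its share of the children: 1/19 = 0.053 with equal sizes, but 1,500/12,900 = 0.116 for a health centre.

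**3. Coverage by simulation.** Two periods per facility; facility effects normal on the logit scale, sized to the plan's ICCs (0.005 referral, 0.05 antibiotics); base rates 3% and 60%. The correlation of a facility's effect between periods was set at 1, 0.8, 0.5 and, as an extreme, 0. There were 6,000 replicates per setting, with exchangeable and independence working correlation, which gave similar results. The GEE code agreed with statsmodels on test datasets.

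Coverage of the nominal 95% interval, uncorrected sandwich with normal quantiles:

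- Kenya, 19 equal facilities: 91.8-92.9%
- Kenya, 19 facilities in the planned mix: 88.6-91.6%
- Senegal, 20 equal facilities: 92.4-93.3%
- Senegal, 20 facilities, size CV about 0.8 (assumed): 89.3-92.0%
- Pooled, 39 facilities: 92.0-93.8%

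Runs with no effect (20,000 replicates, correlation 1 and 0.8) gave 89.5-91.4% in the Kenya mix, a false-positive rate of 8.6-10.5%. With equal sizes they gave 92.4-93.0%, or 7.0-7.6%.

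**4. With a correction.** Mancl-DeRouen standard errors with t on (facilities minus 2) degrees of freedom covered 93.3-96.0% in all the per-country settings.

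**5. The random-intercept model in the same settings.** With 19 facilities and a between-period correlation of 0.5 to 0.8, the random-intercept logistic model covered about 33-50% for antibiotics and 63-85% for referral. It assumes one facility effect shared by both periods and so counts facility-specific drift as information about the intervention.

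**The case against.** Several points against the concern stand.

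- *It is a contingency.* GEE is used only if the quadrature check fails. The documents give no probability of that, and adaptive quadrature for a single random intercept is usually accurate.
- *The SAP does not prescribe the uncorrected standard error.* A reader might infer that the reported intervals will cover only 89-93%. The text does not support that: the figures are conditional on the sandwich with normal quantiles, and the defect is the silence. The silence is not harmless, though. Model-based GEE standard errors mostly covered 94-96% (lowest 87%) when facility effects were the same in both periods, but only 20-88% when they differed.
- *The larger shortfall needs unequal sizes.* A reader might infer a false-positive rate about doubled throughout. That describes only the unequal-size settings; equal sizes give about 7-8%. The documents state no size spread for Senegal, and the Kenya mix is a planning figure, with recruitment reported as lower than anticipated.
- *The change of estimand is disclosed.* SAP 6.2.3 itself calls the GEE odds ratio population-averaged, and SAP 6.2.1 also requires risk differences.

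A further inference is tempting. Quadrature is a way of evaluating the likelihood, so the parenthesis in 6.2.3 is loosely worded, and the natural numerical remedy for a failed check is more points. One might conclude that the random-intercept model should be kept whenever its estimates then settle. Stable integration shows only that the model was fitted accurately. It does not show that facility effects are the same before and after, and step 5 shows how far coverage falls if they are not. Nor does this establish that the primary model is wrong, because the documents give no between-period correlation.

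**Conclusion.** The point holds as a gap in the specification of a fallback. With 19 or 20 facilities per country and the usual uncorrected sandwich with normal quantiles, nominal 95% intervals would cover about 92-93% with equal facility sizes and about 88-92% with the planned Kenya mix. The false-positive rates are about 7-8% and 8-12% in place of 5%. The pooled analysis is less affected, at about 92-94%.

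These figures rest on assumptions outside the documents: the between-period correlation, normal facility effects, no covariates in the simulated model (SAP 6.2.2 adjusts for several) and planned rather than achieved facility sizes. At a correlation of 1, which the random-intercept model implies, the Kenya mix still covers only about 91-92%. The main analysis is untouched unless the fallback is triggered. It is nonetheless worth settling before analysis, because the fallback could carry a primary outcome and the cost is small.

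**What to change.** Add to SAP 6.2.3 that any GEE analysis will use a Mancl-DeRouen or Kauermann-Carroll corrected sandwich standard error, with t intervals and tests on (facilities minus 2) degrees of freedom, and state the working correlation. Count the clusters actually analysed, since SAP 6.2.1 allows clusters to be dropped or combined. Mancl-DeRouen is the better first choice: the 93-96% coverage above was obtained with it. Kauermann-Carroll corrects less: for a Kenya health centre it divides the residual by √(1 − 0.116) = 0.940 rather than by 0.884.

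Do not add a rule that keeps the random-intercept model whenever more quadrature points give stable estimates. Rewording the parenthesis about quadrature and likelihood would be a harmless tidy-up.

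The cost is a few sentences, one software option and wider intervals, with no new data. With 19 equal facilities the widening over the uncorrected interval is about (2.110/1.960) × (19/18) = 1.14, or 14%. In the Kenya mix it is at most (2.110/1.960) × (1/0.884) = 1.22, or 22%, under independence working correlation.

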6.2.4 Pre-planned Sensitivity Analyses

Sensitivity analyses on the primary outcomes are planned and will be conducted:

- ξ On first encounters, which will include only the first enrolment episode of each child during the study period (as some children may attend the facility on more than one occasion). Separate presentations are identifiable from Day0 form as the caregiver is asked whether the child attended previously and within 28 days. This is the minimum number of days required for the disease episode to be considered a new one and not a repeat visit.
- ξ Looking at different referral definitions¹:
 - ο A child will be considered to be referred if, at Day0, the caregiver confirms that the child was urgently referred or the research assistant confirms that an urgent referral advice was recorded for the child. If urgency is unknown from both sources, referral will be assumed to be urgent.

¹ Urgency, as reported by the caregiver, was introduced only in the post-intervention period in Kenya. For the pre-intervention period, urgent referrals will be defined based on the registry alone, as described for the primary analysis.

- A child will be considered to be referred if, at Day0, caregiver confirms that the child was urgently referred *and* the research assistant confirms that an urgent referral advice was recorded for the child.

Additionally, a set of sensitivity analyses shall be carried out based on different definitions of pre and post-intervention periods:

- ξ Pre-intervention and post-intervention defined based on periods of the year that match in the pre and post intervention.
- ξ Pre-intervention defined as primary analysis and post-intervention from country-specific relevant dates (i.e. formal initiation after the strike in Senegal and intensive supervision in Kenya) to the end of data collection.

Sensitivity analyses on the secondary outcomes related to hospitalisation will be conducted looking at different hospitalisation appropriateness (based on different definitions of primary and secondary hospitalisations). Same day (Day0), 3 days and 7 days from Day0 will be used as cut-offs for different primary and secondary hospitalisation definitions.

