5.2 Quasi-experimental pre-post study

A quasi-experimental pre-post study, comparing clinical care of children attending primary care facilities in a pre-intervention (baseline period) with those attending facilities following introduction of the intervention (intervention period). The 6 – 8 month baseline period is followed by a 9 – 12 month intervention period to allow for evaluation of change over time

from introduction of intervention and for some seasonal overlap in pre- and post-intervention periods.

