7.2.4 Data quality assurance and control

Quality assurance activities across all studies will be more intense during study start-up to ensure quality data practices are instituted from the start of the trial. Further details will be given in the DMP and SOPs.

All research assistants will be trained to provide information and seek written consent using the information and consent form. Separate trainings will cover all aspects of quantitative data collection and all aspects of qualitative data collection. A competency assessment using scenarios will be done before commencing field work.

Data reconciliation between the different visits of the same child will be one of the most crucial data quality activities in the pre-post study. Specific procedures will be developed for this purpose. To identify repeat visits of children that may re-attend the study facility where they enrolled, or any other study facility during the follow-up period, participants will be given a study card (or sticker) with a unique ID number. Retrospective search for data at referral level will be restricted to facilities within the geographical area where the study is running and will be targeted to include only children reported to have attended hospital by the caregiver at follow-up and those lost to follow-up. The name of the referral facility will be requested during the follow-up call. If available, it should further restrict the scope of the search and the probability of negative matches when cross-checking the participant identity. Children who re-attend any study facility more than 28 days after their previous enrolment will be enrolled for the new disease episode and given a new ID number. If available, the old ID number will be recorded to facilitate linking of the different disease episodes. Data to be potentially reconciled will be flagged by automated cross-check of a set of personal identifiers. Given that personal identifiers may not be identically recorded at each visit, fuzzy matching methods will be used to calculate a score of similarity between records and likelihood that they relate to the same child. Reconciliation of records with high similarity scores will be manually validated.

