We will conduct the primary analysis on all visits (for visits by the same child, this implies visits greater than 28 days apart as per the exclusion criteria). However, we will conduct a sensitivity analysis excluding repeat visits of an individual child within the same quarter, to address the possibility that outcomes of children attending for more than one disease episode are correlated and impact the interpretation of the study. Due to the challenge in correctly identifying all repeated visits, the fairly low likelihood of repeat visits (based on available literature) and the acuity of the majority of sick child visits, we do not expect these analyses to produce very different results. We will conduct sensitivity analyses for measured and unmeasured confounders over time to assess robustness of the findings, which will be detailed in the SAP.

An exploratory interrupted time series analysis will be conducted to assess change over time.

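### The first-encounter sensitivity analysis keeps each child's first enrolment over the whole study, so children enrolled in both periods stay in the pre set and drop out of the post set

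*SAP*

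**What the plan says.** Protocol 7.3.1 sets the primary analysis on every eligible visit: "We will conduct the primary analysis on all visits". Because episodes of the same child may be correlated, it adds a check: "we will conduct a sensitivity analysis excluding repeat visits of an individual child within the same quarter". It expects little difference, since repeats are thought to be fairly uncommon, are hard to identify completely, and most visits are for acute illness.

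SAP 6.2.4 plans a check on the same issue with another rule. It uses first encounters, "which will include only the first enrolment episode of each child during the study period", and identifies separate presentations from a Day 0 question to the caregiver about previous attendance. SAP 1.1 says that the SAP follows the protocol unless it details otherwise. The change of rule is not mentioned as a change and no reason is given.

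Three other statements matter:

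- Protocol 5.2, on the order of the periods: "The 6 – 8 month baseline period is followed by a 9 – 12 month intervention period".
- Protocol 7.2.4, on re-enrolment: "Children who re-attend any study facility more than 28 days after their previous enrolment will be enrolled for the new disease episode".
- SAP 6.2.1, on the boundary between periods: "As training was staggered for the facilities, the definitions above will be applied at the facility level".

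**The concern.** The periods follow one another at the same facilities, so for a child enrolled in both, the first enrolment is normally a pre-intervention one. A rule that keeps one record per child over the whole study then assigns that child to the pre set alone. The pre set still contains children who will come back. The post set contains only children not previously enrolled.

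The study has no concurrent control, so its comparison rests on the two samples being alike. A check meant to isolate the effect of correlated episodes would also change who is compared with whom. If its estimate differed from the primary one, the reader could not tell whether correlation or selection was the cause.

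**Working it through.** **1. The plan's own figure.** The documents give no figure for this analysis. The initial sample size in protocol 6.6.1 is reproduced here because step 5 uses it. Referral of 3% against 4.5%, power 80%, alpha 0.05 (taken as two-sided from SAP 4.1) needs 2,518 children per period before clustering. The design effect is 1 + (m − 1) × ICC, with ICC 0.005.

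- Kenya, m = 690: 1 + 689 × 0.005 = 4.445; 2,518 × 4.445 = 11,193; divided by 690 = 16.2, so 17 facilities and 11,730 children.
- Senegal, m = 510: 1 + 509 × 0.005 = 3.545; 2,518 × 3.545 = 8,926; divided by 510 = 17.5, so 18 facilities and 9,180 children.

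Both match the plan.

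**2. Which records each rule keeps.** Repeat enrolments within a period are taken to fall in different quarters. Entries are pre / post records kept.

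| Child's enrolments | First over study (SAP) | First within each period | First within each quarter (protocol) |
|---|---|---|---|
| 1 pre, 1 post | 1 / 0 | 1 / 1 | 1 / 1 |
| 2 pre, 1 post | 1 / 0 | 1 / 1 | 2 / 1 |
| 1 pre, 2 post | 1 / 0 | 1 / 1 | 1 / 2 |
| 2 post only | 0 / 1 | 0 / 1 | 0 / 2 |

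Only the SAP rule removes a child from one period because of enrolment in the other. This needs no assumed figure.

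**3. How unequal the losses could be.** This is a visit simulation with 7 months pre and 10 months post (within the planned ranges), a 28-day gap before re-enrolment, exponentially distributed visit rates between children, and quarters counted from the start of each period. The mean visit rates are assumptions. Entries are the percentage of enrolments dropped, pre / post.

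| Visits per child-month | SAP rule | First within period | First within quarter |
|---|---|---|---|
| 0.02 | 9.6 / 31.5 | 9.6 / 12.9 | 2.3 / 2.2 |
| 0.05 | 20.1 / 56.2 | 20.1 / 27.6 | 5.6 / 5.7 |
| 0.10 | 31.9 / 74.7 | 31.9 / 41.7 | 9.8 / 10.1 |

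The absolute levels say nothing about this study, because the rates are invented. The contrast between the rules is the result. The smaller imbalance of the within-period rule arises because the post period is longer.

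**4. What the selection could do to the estimate.** Let s be the share of enrolments from both-period children and r their risk relative to other children. Both are assumed, and taken as equal in the two periods. With no intervention effect and overall risk p, the other children have risk p / (1 + s(r − 1)). The post set falls to that risk. The pre set is taken to stay at p, which ignores the later pre repeats that are also dropped. The calculation is unadjusted.

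| Outcome, p | s | r | Post risk after filter | Odds ratio |
|---|---|---|---|---|
| Referral, 3% | 10% | 1.25 | 3 / 1.025 = 2.93% | 0.975 |
| Referral, 3% | 20% | 1.5 | 3 / 1.10 = 2.73% | 0.907 |
| Referral, 3% | 20% | 0.8 | 3 / 0.96 = 3.12% | 1.043 |
| Antibiotic, 60% | 10% | 1.25 | 60 / 1.025 = 58.5% | 0.941 |
| Antibiotic, 60% | 20% | 1.25 | 60 / 1.05 = 57.1% | 0.889 |
| Antibiotic, 60% | 20% | 0.8 | 60 / 0.96 = 62.5% | 1.111 |

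If r = 1 the odds ratio is 1.00 whatever s is.

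**5. Power.** At the sizes in step 1, with the pre sample unchanged and the post sample cut by 5–30%, power for referral is 81.6–80.2% in Kenya and 80.8–79.0% in Senegal. Without a cut it is 81.8% and 81.1%. For losses in that range the issue is comparability, not power.

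**The case against.** The best defence of the SAP rule is that it is the only one of the three that removes all identified within-child correlation, which is the purpose protocol 7.3.1 states. Both alternatives leave a child's pre and post records in the comparison. That stands: the choice is a trade-off, and it is a reason to keep the whole-study version as a companion analysis.

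The protocol leaves detail to the SAP, so refining a rule is legitimate. That also stands. What is missing is a statement that the rule changed and why.

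The phrase about the study period might be meant as each period. The singular, the SAP's separate names for the pre- and post-intervention periods, and its use of the same phrase in the facility exclusion criteria (SAP 5.2) favour the whole-study reading. If each period was meant, a few words settle it.

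The models adjust for age, illness duration, presentation, previous care and previous treatment (SAP 6.2.2), which may absorb part of any difference. No listed covariate records prior enrolment or attendance frequency, so full correction cannot be assumed.

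A reader might infer more than the documents support:

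- **That only post records are ever lost.** A child with several pre enrolments also loses the later ones, and staggered training allows a rare child seen first at a facility already in post and later at one still in pre.
- **That the post set has never attended before.** It has only never been enrolled before; attendance before data collection or without consent does not count.
- **That agreement with the primary result would be worthless.** It would be informative unless selection and correlation happened to offset each other.

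**Conclusion.** The point holds for one sensitivity analysis. Under the whole-study reading, the filter treats both-period children differently pre and post. The protocol's rule does not, and the departure is undeclared.

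It would be tempting to conclude that the trial's main result is biased, or that the check will understate referral. Neither follows. The primary analysis uses all visits and does not pass through this filter. The direction depends on whether repeat attenders have higher or lower risk than other children, and the size depends on that and on how many there are. The documents give neither quantity and describe repeats as uncommon. The ranges in step 4, about 0.91 to 1.04 for referral (s 10–20%, r 0.8–1.5) and 0.89 to 1.11 for antibiotics (s 10–20%, r 0.8–1.25), illustrate what assumed values would produce with no true effect. They are not estimates for this study. This is a worthwhile, inexpensive improvement to a robustness check.

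**What to change.** In SAP 6.2.4, define the check as either the protocol's within-quarter exclusion or the first enrolment of each child within each period, applied in the same way pre and post. The within-quarter rule was the more balanced in step 3. If it is used, define quarters so that none straddles a facility's changeover date; otherwise a child seen on both sides of it within one quarter would again lose the post record.

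Identify repeats with the study ID and the record-matching procedure in protocol 7.2.4, not the caregiver question alone. Report the number of children enrolled in both periods and the number of records dropped in each. State the departure from protocol 7.3.1 and the reason if a different rule is kept.

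The cost is a wording change and a different filter on existing data. The downside is that a child's pre and post records both remain, so some within-child correlation is left. Reporting the whole-study version alongside, or modelling child-level correlation, covers this.
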